## **Randomization and Intervention**

Block randomization in blocks of 8 was used to assign participants to 1 of 2 groups: Group 1 received bottle A (topical probiotic in soybean concentrate) and Group 2 received bottle B (placebo). Both groups received secondary dressing with standard wound care with wet-to-dry dressings. The assigned topical treatment was applied directly to the ulcer twice daily throughout the treatment phase.

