## **Outcomes and Data Collection**

Baseline demographic data, medical history, comorbidities, current treatments, and wound characteristics were recorded at enrolment. Participants were evaluated weekly or biweekly for up to 24 weeks or until complete wound healing, whichever occurred first. At each visit, wound surface areas were measured and documented using standardized digital photography. Adverse events were assessed and documented at each visit. Debridement, when necessary, was performed as part of routine clinical care and recorded.

The **primary outcome** was the proportion of wounds achieving complete healing within 24 weeks. Complete wound healing was defined as full re-epithelialization without drainage or dressing requirements. Wound healing was assessed jointly by the treating plastic surgeon and wound care nurse. Due to resource constraints, independent blinded assessors were not employed.

**Secondary outcomes** included percentage reduction in wound area, wound recurrence rates, incidence and nature of adverse events, and the need for additional surgical intervention. Participants who achieved wound healing were followed at 2- and 12-weeks post-healing to monitor for recurrence or complications.

Unblinding of treatment allocation was permitted only in the case of a serious adverse event (SAE) in which treatment knowledge was required for patient safety. All unblinding events were documented and reviewed by the data monitoring committee. Otherwise, treatment codes remained concealed until study completion.

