## **Statistics**

All analyses were performed using IBM® SPSS® Statistics V25. Continuous variables were summarized using means and standard deviations. Categorical variables were expressed as frequencies and percentages. Paired *t* tests were used to evaluate differences in continuous variables. Chi-square ( $\chi^2$ ) tests were applied for comparisons of categorical variables. Survival outcomes were assessed using Kaplan–Meier analysis and Cox proportional hazards regression modelling. All tests were two-sided, and *p* values  $< 0.05$  were considered statistically significant.

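### The survival analysis has no event definition, censoring rule or competing-event method; if death or loss of the ulcer site is censored, Kaplan-Meier overstates the proportion healed

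*Combined protocol and SAP*

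**What the plan says.** The time-to-event plan is one sentence in the Statistics section: "Survival outcomes were assessed using Kaplan–Meier analysis and Cox proportional hazards regression modelling". It gives no event, time origin, censoring rule or competing-event method.

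The other relevant text is in Outcomes and Data Collection:

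- The primary outcome is binary: "the proportion of wounds achieving complete healing within 24 weeks". The Statistics section does not assign it a test by name, but its general rule is that chi-square "tests were applied for comparisons of categorical variables". The denominator is not defined.
- Follow-up: "Participants were evaluated weekly or biweekly for up to 24 weeks or until complete wound healing, whichever occurred first". Healing and week 24 are the only ends of observation mentioned.
- Healing: "Complete wound healing was defined as full re-epithelialization without drainage or dressing requirements". The text does not say how an ulcer removed by surgery counts.
- Among the secondary outcomes is "the need for additional surgical intervention". No procedure is named, and no link to the healing analysis is made.

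The text available for review mentions neither death nor amputation. Table 1, which holds the full eligibility criteria, is cited but not reproduced there.

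**The concern.** Healing is the natural event for these curves: it is the primary outcome, and it ends follow-up. A participant with a diabetic foot ulcer may die, or lose the ulcer site to surgery, before healing. Kaplan-Meier has only two states, event and censored. Without a rule, such a participant would ordinarily be censored at the last visit. Censoring assumes that the participant would have gone on to heal at the same rate as those still under observation, and that is impossible here. One minus Kaplan-Meier then estimates healing in a hypothetical setting where nobody dies or loses the site, not the proportion who healed.

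Two things are at stake. The curve at week 24 can read higher than the primary proportion in the same report, with no explanation. And if the arms differ in competing events, the curves can favour the arm in which more participants died or lost the ulcer site.

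**Working it through.** **Inputs.** From the documents: a 24-week horizon, the methods named (Kaplan-Meier, Cox), and weekly or biweekly visits. The documents give no healing rate, competing-event rate, dropout, sample size or power, so there is no planned figure to reproduce. Assumed: 30% to 70% truly healed (F1), and 0% to 20% observed to die or lose the site while unhealed (F2), both by week 24.

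**Formula.** Take constant cause-specific hazards and no other dropout.

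- Total cumulative hazard to week 24: Λ = −ln(1 − F1 − F2).
- Healing share: Λ1 = Λ × F1/(F1 + F2).
- With competing events censored: 1 − KM(24) = 1 − exp(−Λ1).

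**Worked case, F1 = 50%, F2 = 10%.** Λ = −ln(0.40) = 0.9163. Λ1 = 0.9163 × 0.50/0.60 = 0.7636. 1 − KM = 1 − exp(−0.7636) = 53.4%, which is 3.4 points above the 50% who healed. A simulation of 200,000 participants with biweekly visits gave 50.2% healed and 1 − KM of 53.4%.

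**Range.** Excess of 1 − KM over the true proportion healed, in percentage points:

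| Truly healed | F2 = 0% | 2% | 5% | 10% | 20% |
|---|---|---|---|---|---|
| 30% | 0 | 0.3 | 0.9 | 1.8 | 4.0 |
| 50% | 0 | 0.6 | 1.6 | 3.4 | 7.7 |
| 70% | 0 | 1.0 | 2.6 | 5.5 | 13.3 |

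**Timing.** Constant hazards are not essential. With F1 = 50% and F2 = 10%, if all competing events come after the last healing, 1 − KM is 50.0% and the gap is zero. If all come before the first healing, it is 0.50/0.90 = 55.6%.

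**Between arms.** With 50% healed in both arms and competing events of 5% against 15%, the censored curves read 51.6% and 55.4%. That is a false advantage of 3.8 points for the arm with more deaths or site losses. With 55% against 40% healed and the same 5% against 15%, the curves read 56.8% and 44.1%, so a true 15.0-point difference shrinks to 12.8 (unrounded 56.83 − 44.05).

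**Against the primary proportion.** If every randomized participant is in the denominator, the proportion is F1 and lies at or below 1 − KM. If those who died or lost the site are dropped, it is F1/(1 − F2): 0.50/0.90 = 55.6%, above the curve's 53.4%. The direction of any mismatch therefore depends on a denominator that the plan does not state.

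**After the fix.** Kept at risk as unhealed to week 24, these participants leave the Kaplan-Meier curve at F1 and the gap is zero, provided there is no other dropout. To see how far dropout breaks this, take net risks (each as if the other event did not occur) of 60% for healing and 20% for competing events. The cumulative hazards are 0.9163 and 0.2231, and the cumulative incidence of healing is 0.9163/(0.9163 + 0.2231) × (1 − 0.40 × 0.80) = 54.7%. Simulated with 30% independent dropout, the recoded curve fell less than one point below this.

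**The case against.** The strongest reply is that the plan states no wrong rule. It does not say that the curves are for healing, and recurrence is also followed after healing. It does not say that death or amputation is censored. As written, it is compatible with carrying unhealed participants to week 24, which is one of the remedies proposed here. The surgical outcome names no procedure and need not end follow-up or prevent healing. Eligibility excludes exposed bone or tendon, so competing events may be few. The primary comparison appears to be a chi-square test on a binary outcome, which leaves Kaplan-Meier and Cox in a supporting role. A cause-specific hazard ratio is a legitimate quantity.

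Most of this stands, and it sets the limits of the point. The defect is an unstated rule combined with a method whose usual default is unsuitable, not an error written into the plan. What does not stand is the inference that the gap is harmless: the plan names no competing-event method, and a reader cannot tell from it what the curves estimate.

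A reader might infer that the curve is bound to contradict the primary proportion. The documents do not support that. The two agree when no such event precedes a later healing and there is no other censoring. Ordinary dropout can also separate them, so a mismatch alone would not prove competing-risk bias.

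**Conclusion.** The point holds conditionally. If the event is healing and participants who die or lose the ulcer site are censored, 1 − KM is at least the proportion healed, and strictly above it whenever such an event precedes a later healing. On assumed rates the excess is 1 point or less at 2% competing events, about 1 to 3 points at 5%, and 4 to 13 points at 20%, depending on how many heal. A false between-arm contrast needs competing events to differ between arms, and the documents give no basis for expecting that.

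A reader might also conclude that the primary result is biased. Nothing in the documents shows this. The primary outcome is affected only in that its denominator rule is missing too. The change is worth making, because it replaces a method that answers a different question with an accepted one at little cost.

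**What to change.** 1. State in the Statistics section that the event is complete healing as defined under Outcomes and Data Collection, and give the time origin and the censoring rule.
2. Replace the Kaplan-Meier healing curve with the cumulative incidence of healing (for example Aalen-Johansen, with Gray's test), treating death and loss of the ulcer site as competing events. In SPSS V25, keeping these participants at risk as unhealed to week 24 gives the same curve when there is no other dropout, and approximately the same otherwise.
3. Count the same participants as unhealed in the denominator of the primary proportion, so that the two figures agree.
4. Label a Cox hazard ratio that censors these events as cause-specific, and one fitted to the recoded data as a subdistribution hazard ratio.
5. Tabulate competing events by arm.
6. Disclose the change as made after the trial ended.

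The cost is a small recode, some wording, and healing curves that may look slightly less favourable. It assumes that dates of death and of loss of the site can be recovered from the adverse-event and surgery records. The documents say that adverse events were documented at each visit and list surgery as an outcome, but they do not mention these dates.
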